Standard BCHD Linkage Services. The 2007 Maryland HIV/AIDS Reporting Act requires that HIV cases be reported by name. Laboratories are required to report HIV positive tests within 48 hours to the BCHD through PRISM, a morbidity and case management software. Data from PRISM is used to identify new HIV diagnoses and refer cases to a BCDH Disease Intervention Specialist for contact investigations and referral to linkage services. In addition, the Maryland Department of Health (MDH) HIV Surveillance Branch receives laboratory-based reports with results indicating HIV infection (including HIV diagnostic tests, CD4, HIV viral loads, and HIV genotype and phenotype tests) through the enhanced HIV/AIDS Reporting System (eHARS). Using this data, MDH generates weekly “Never in Care” and “Out of Care” lists for BCHD. Guided by these data, the BCDH linkage team contacts patients by phone or in person to connect them to care. Providers can also request assistance from the BCHD LTC program to link patients newly diagnosed or re-engage those lost to HIV care by contacting the LTC team. Therefore, the BCHD linkage officers attempt to contact and provide linkage services to all Baltimore residents newly diagnosed with HIV or who are presumed to be Out of Care or Never in Care, as identified through surveillance data or by referral from providers. Patients who agree to be linked to care by linkage officers are provided a same-day appointment and warm handoff to clinical care (the outreach worker drives the patient to the clinic of his or her choice). After the patient is seen by a provider, the linkage officer can assist with retention to the second appointment, but after the two initial appointments, the LTC officer is no longer involved in the case unless the patient appears again in the MDH Out of Care report at a later time or is referred by a provider. Linkage officers record patient encounters, and linkage attempts and outcomes in PRISM.

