Laboratory Data	HIV surveillance data (Viral load and date) is provided by the BCHD and uploaded to emocha platform	
Laboratory Alerts	Support staff is alerted if participant in the intervention arm has not had a viral load in > 4 months or if the viral load is detectable (> 200 copies/ml)	Support staff contacts participant if alerted
Appointment Alerts	Support staff alerted if no upcoming appointment is documented in the emocha app or the patient responds "No" or does not respond to the question "Did you go to your appointment yesterday" or patient requests help rescheduling appointment	Support staff contacts participant if alerted
Patient initiated messages	Support staff alerted when participant sends message	Support staff contacts participant if alerted

Study Design.

This study is a pragmatic individual randomized trial comparing standard BCHD linkage services or clinic-based linkage and retention and care support services to mLTCR services. The study will not be masked to participants or support staff due to practical considerations, but all data analysis related to Aim 1 will be conducted in a blinded fashion. Figure 2 describes the study design.

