
HIV Surveillance Data Flow. HIV laboratory data (dated viral load) will be used to drive emocha app alerts and for evaluation of primary outcomes. A list of the individuals who have consented to the study (including those recruited in the clinics) will be provided to the BCDH on a weekly basis. The BCHD will send this information to the Maryland Department of Health HIV Surveillance Branch. MDH will generate a weekly report of HIV viral load test results and dates and send this information to the BCDH. The BCDH will share this information with emocha so that it can be uploaded to the emocha platform. Alerts to participants will not include HIV-specific information. HIV surveillance data will be uploaded to the

emocha platform for all participants (intervention and control) and used for data analysis. However, this data will be integrated into the emocha algorithms and alerts only for participants in the intervention arm. Data on all participants will be exported from emocha to JHU secure servers for data analysis.

A backup system will be implemented in the event the MDH or BCHD is unable to generate and/or share the weekly HIV viral load test results. Study team members will access viral load data through health provider records and upload data directly from JHU secure servers to the emocha platform.

Laboratory Assessments. There will be no study-associated laboratory assessments. All laboratory assessments will be conducted as part of clinical care and reported to BCHD HIV surveillance databases (eHARS and PRISM). We will consider those with a suppressed viral load (HIV RNA <200 c/mL) to be fully engaged in HIV care. While some individuals are able to maintain immune control of HIV in the absence of ART, this occurs in <1% of infected persons.

Randomization plan. The study Statistician will generate a randomization schedule to assign 250 participants to each of the study arms with an arbitrary labelling of the arms. All but the data manager will be blinded to the arm assignment to the arbitrary labels initially. When a linkage officer makes the initial contact with an eligible participant /patient, they will introduce the study and if consent to participate is obtained, the officer will telephone the data center to obtain an arm assignment and proceed to enroll the participant. All data analysis will be conducted in a blinded fashion, but the linkage officers and participants cannot be masked from the intervention.

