- b. Secondary outcome variables.
 - 1. Retention in care: Viral load or CD4 count reported in eHARS within a 6 month window of 12 month follow up period (i.e. 3 months before or after 12 month follow up)
 - 2. Mortality: Death occurring within a 6 month window of 12 month follow up period (i.e. 3 months before or after 12 month follow up)
 - 3. Implementation outcomes will include:
 - a. Proportion of out of care or newly diagnosed HIV-infected patients contacted by support staff.
 - b. Frequency of contacts between support staff and patients.
 - c. Qualitative assessments from in-depth interviews with support staff, BCHD/clinic officials, and study participants
 - d. Client satisfaction surveys
- c. Statistical plan including sample size justification and interim data analysis.

Statistical Analysis. For the study's main outcome, we will conduct a test for the equality of proportions of virologically suppressed/not suppressed or missing VL individuals at 12 months between the two study arms, in line with the randomized design of the study. Secondary to this, and to adjust for any residual confounding, we will conduct a logistic regression using individual outcomes (yes/no suppressed) with study arm as a main predictor and adjusting for patient demographic characteristics, socio-economic status at baseline, and other factors. A subgroup analysis will be conducted to assess the effects of the intervention among African-American and people of Hispanic/Latino descent.

Secondary outcomes analysis. An evaluation of the differences in retention in care and participant mortality will follow the same analytical approach as for the main outcome. That is, we will test for the difference in proportions between the 2 arms and a logistic regression will be conducted adjusting for study arm and patient characteristics.

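### The primary test leaves out pre-randomisation viral load; adjusting for it would be a cheap improvement with a modest gain in precision

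*Combined protocol and SAP*

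**What the plan says.** The primary analysis is a comparison of two proportions: "we will conduct a test for the equality of proportions of virologically suppressed/not suppressed or missing VL individuals at 12 months" (7c, Statistical Analysis). A participant with no 12-month viral load counts as not suppressed. A secondary logistic regression follows, "adjusting for patient demographic characteristics, socio-economic status at baseline, and other factors". Entry viral load is not in that list, and the last item is left open.

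Under Randomization plan (4a), the statistician will "generate a randomization schedule to assign 250 participants to each of the study arms". No stratification is mentioned. Section 5 sets no viral load criterion and admits new diagnoses, people out of care and clinic referrals, so entry status can vary.

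The raw material for the covariate is largely in place:

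- Under Standard BCHD Linkage Services, the state health department "receives laboratory-based reports with results indicating HIV infection (including HIV diagnostic tests, CD4, HIV viral loads, and HIV genotype and phenotype tests".
- Table 2 records that "HIV surveillance data (Viral load and date) is provided by the BCHD and uploaded to emocha platform".
- HIV Surveillance Data Flow says these data go to the "emocha platform for all participants (intervention and control) and used for data analysis".
- As a backup, "Study team members will access viral load data through health provider records".

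**The concern.** For a binary endpoint, the same variable measured before randomisation is usually among the strongest predictors available. Here it has no stated role in allocation, in the primary test or in the secondary model. A chance difference between arms in entry suppression would therefore pass into the primary estimate, and no planned analysis names the variable that would correct it. The secondary model's open list of covariates does not settle this: a term added there after results are seen is open to challenge.

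What is at stake is precision. Randomisation protects the unadjusted test from bias and keeps its type I error.

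**Working it through.** **The plan's own figure.** Inputs from 7c, Power Calculations: 33% v 46%, 80% power, 5% alpha. Sidedness is not stated; two-sided reproduces the result. With mean proportion 0.395:

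n per arm = [1.96·√(2·0.395·0.605) + 0.8416·√(0.33·0.67 + 0.46·0.54)]² / 0.13² = 220.8, so 221 per arm and 442 in total. This matches. By the same pooled-variance formula, power is 80.0% at 221 per arm and 84.7% at 250.

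**Gain from adjustment.** Let s be the share suppressed at entry and p1 their 12-month suppression rate under control. Holding the control rate at 33%, the rest have p0 = (0.33 − s·p1)/(1 − s). The variance explained is R² = s(1 − s)(p1 − p0)²/(0.33·0.67). Adjusted power is that of 250/(1 − R²) per arm. If half of everyone has no result on file, at random, R² halves. All values of s and p1 are assumptions.

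| s | p1 | p0 | R² | Effective n per arm | Power | Power, half with no result |
|---|---|---|---|---|---|---|
| 0.05 | 0.55 | 0.318 | 0.012 | 253 | 85.1% | 84.9% |
| 0.05 | 0.70 | 0.311 | 0.033 | 258 | 85.8% | 85.2% |
| 0.10 | 0.55 | 0.306 | 0.024 | 256 | 85.5% | 85.1% |
| 0.10 | 0.70 | 0.289 | 0.069 | 269 | 87.1% | 85.9% |
| 0.20 | 0.65 | 0.250 | 0.116 | 283 | 88.7% | 86.7% |

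**Confidence interval.** Half-width = 1.96·√[(0.33·0.67 + 0.46·0.54)/n]. This is 8.5 points at n = 250, 8.4 at 253 and 8.0 at 283.

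**Chance imbalance.** The 95% range of the shift in the unadjusted estimate is ±1.96·√[2s(1 − s)/250]·(p1 − p0). It is ±0.9 points for (s, p1) = (0.05, 0.55), ±1.5 for (0.05, 0.70), ±2.2 for (0.10, 0.70) and ±2.8 for (0.20, 0.65), against a 13-point target.

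**Simulation.** Four of these scenarios, all but (0.10, 0.55), were simulated with 6,000 trials of 500 each. The model was logistic with arm and three-level viral load, and the estimate a standardised risk difference with influence-function standard error.

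- With half of the non-suppressed having no result, adjusted power was 85.2%, 86.2%, 87.1% and 88.8%, against 84.6%, 85.3%, 84.9% and 84.8% unadjusted.
- With half of everyone having no result, it was 84.9%, 85.3%, 85.8% and 86.7%, against 84.5-84.8%.
- The mean risk difference was 0.129-0.131 adjusted and 0.130-0.131 unadjusted, so the estimand is unchanged.
- Type I error was 4.7-5.4% adjusted and 4.4-5.6% unadjusted (Monte Carlo standard error 0.3 points).

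**The case against.** **The plan is sound and the gain may be close to nil.** The unadjusted test is a deliberate choice, the sample size is correct for it, and enrolling 500 already gives 84.7% power because nobody is dropped for a missing result. The entry routes point to few suppressed participants, and at 5-10% the power gain is only 0.4-2.4 points. Nothing in the documents supports the 20% scenario. All of this stands, and it is why the point is an improvement and not a correction.

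**The imbalance figure is not a separate harm.** Correct. √(8.49² − 2.8²) = 8.0 and √(8.49² − 0.9²) = 8.4, which are the adjusted half-widths. It is the same variance gain on another scale and should not be counted twice.

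**A group with no result on file would pool new diagnoses with people long out of care.** It would, but a further simulation with mixed prognosis inside that group still showed a small power gain with type I error near 5%. Entry route could be considered as a further term.

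**The rule for merging sparse levels could undo the adjustment.** With 5% suppressed and half lacking a result, about 500 × 0.05 × 0.5 = 12.5 people fall in the <200 level, close to a threshold of 10. This happens only where there is almost no gain to lose.

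**The data may not reach back before consent.** This stands in part. The weekly request begins when "A list of the individuals who have consented to the study (including those recruited in the clinics) will be provided to the BCDH", and no look-back is stated. Provider records are described only as a fallback for when the surveillance feed fails, so routine use for baseline status would be new.

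**Conclusion.** The concern holds as a worthwhile, low-cost improvement. It is certain that entry viral load has no named role. The size of the benefit is uncertain because it rests on entry suppression rates and 12-month rates that the documents do not give. Over the assumed range, power at 250 per arm rises by 0.4 to 4.0 points, or by 0.2 to 2.0 points if half of participants have no prior result at random. The half-width shrinks by about 0.1 to 0.5 points. The gain is larger only if more participants are suppressed at entry. In none of these scenarios did the calculated power fall, and simulated type I error stayed near 5%.

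**What to change.** In 7c, make the primary estimate and test a standardised (marginal) risk difference from a logistic model with two terms: arm, and pre-randomisation viral load status (<200, ≥200, none on file).

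- Define status as the last result dated on or before randomisation within a stated look-back window. Twelve months is one option: the described clinic flags people with no visit for more than 8 months, and a 6-month window would tend to place them in 'none on file'.
- Use the same sources and the same rule in both arms.
- State, before arm labels are broken, that a level with very few participants (for example fewer than 10) is merged with ≥200.
- Keep a missing 12-month viral load as not suppressed.
- Keep the unadjusted two-proportion test as supporting, and rule out switching between the two.
- Put the same viral load term in the secondary logistic model.

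The cost is analysis-plan text, one derived baseline variable, and an explicit extension of the surveillance request or provider-record check to results dated before consent. No visit or laboratory test is added, in keeping with the aim in 4b of limiting study contact to baseline.
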